2.0 STUDY SUMMARY

Name of Sponsor(s):	Compound:	
Cerevance Beta, Inc.	CVN424	
Title of Protocol: A Phase II, Randomized, Double-Blind, Placebo-Controlled, Multicenter Study of CVN424 in Parkinson's Disease Patients with Motor Fluctuations	IND No.: 138119	EudraCT No.: Not applicable
Study Number: CVN424-201	Phase: 2	

Study Design:

This is a phase 2 study, randomized, double-blind, placebo-controlled, multicenter study of oral CVN424 at two dose levels (low-dose 50 mg, high-dose 150 mg) in Parkinson's disease (PD) patients with motor fluctuations. The overall study design is depicted and described below:

Note: Not all efficacy or safety assessments are performed at all study visits.

Approximately 135 male and female subjects with Parkinson's disease, on a stable dosage of levodopa but with an average of ≥ 2 h total OFF time/day and not less than 1 h per day, will be enrolled. Following baseline safety and efficacy assessments, subjects will be randomized to receive once-daily doses of either low-dose CVN424, high-dose CVN424, or matching placebo. The planned low-dose and high-dose levels will be 50 and 150 mg CVN424 per day, respectively. All subjects not randomized to placebo will initiate treatment with 50 mg CVN424 on Day 1; the low-dose arm will continue to receive 50 mg per day, while the high-dose arm will increase their daily dosage to 150 mg CVN424 beginning on Day 8 ± 2 days and continuing thereafter. Investigator or their delegate will manage incident AEs according to their medical judgment. Study drug will be self-administered each morning as an oral suspension. Subjects will continue their other PD medications.

Subjects will follow the study schedule presented below. Dosing on Day 1, Day 8, and Day 22 visits will be observed at the study site by Investigator or their delegate. For Visit Days 8 and 22, dosing of study drug (but not subjects' other medications) will be deferred until after collection of a blood sample for determination of the study drug "trough" concentration.

	Baseline & Random-ization	reatment ^b	Follow-up ^c
--	---------------------------	-----------------------	------------------------

Study No. CVN424-201 Page 10 of 73

Protocol v. 4.0 14 July 2021

Consent, Eligibility	Patient Motor Diary at Home	Study Visit	Study Visit	Study Visit	Study Visit	Study Visit	Study Visit	Final Study Visit
Days -28 to -1	Days -2 & -1	Day 0	Day 1 d	Day 8 ±2 days	Day 15 ±2 days	Day 22 ±2 days	Day 27 ±1 day	Day 35 ±2 days

- (a) Screening activities must occur within 28 days of randomization, but may be completed in fewer than 28 days. Screening days are nominally called Day -28 to Day -1 but will not necessarily correspond numerically to the calendar days prior to the Baseline Visit. By the same convention, the Patient Motor Diary will be recorded at home over 2 consecutive days during screening, but not necessarily on the 2 days immediately prior to the Baseline visit.
- (b) Study drug supply will be dispensed (as suspension in amber colored bottles) on Day 1 and at subsequent weekly study visits. Subjects will return empty and unused bottles to site. Study drug will be self-administered each morning as an oral suspension. For Visit Days 8 and 22, dosing of study drug (but not subjects' other medications) will be deferred until after collection of a blood sample for determination of the study drug "trough" concentration.
- (c) Subjects who have abnormal, clinically significant (CS) findings at the Final Study Visit may be asked to return to the clinic subsequently to ensure appropriate safety follow-up.
- (d) By convention, Day 1 will be the first day of treatment. It will not necessarily occur on the calendar day following the baseline and randomization visit.

Follow-up assessments will occur approximately 7 days after the final (Day 27 ±1 day) dose.

Study committees:

None. (Review of incident and cumulative safety data and findings is the responsibility of the Medical Monitor and sponsor's Responsible Medical Officer.)

Safety stopping rules:

If any of the following occur, the Medical Monitor and Sponsor's Responsible Medical Officer will review the relevant data, including unblinded data if deemed necessary, and decide whether it is safe to suspend dosing or continue dosing at either the planned or alternative dose levels or decides to prematurely terminate the study:

- ^{1.} Four or more subjects receiving CVN424 experience the same type of serious or Medically Significant event deemed related to study drug.
- ^{2.} Three or more subjects receiving CVN424 experience alanine aminotransferase (ALT) and/or aspartate aminotransferase (AST) elevations >5 × upper limit of normal (ULN) in the absence of a concomitant bilirubin increase (see below).
- One or more subjects receiving CVN424 experience ALT and/or AST elevations >3 ×ULN in the presence of a total bilirubin increase >2 ×ULN or an international normalized ratio (INR) >1.5 without findings of cholestasis or other alternate etiology to explain the elevations (i.e., "Hy's Law cases").
- Two or more subjects receiving CVN424 experience ALT and/or AST elevations >3 ×ULN with the appearance of fatigue, nausea, vomiting, right upper quadrant pain or tenderness, fever, rash and/or eosinophilia (>5%).

Primary Objective:

To assess the safety and tolerability of CVN424 when administered as daily oral doses for 28 days, adjunctive to levodopa, in subjects with Parkinson's disease and motor fluctuations.

Study No. CVN424-201 Page 11 of 73

Protocol v. 4.0 14 July 2021

Secondary Objectives:

- To assess potential efficacy of CVN424 adjunctive to levodopa in alleviating symptoms of PD
- To assess CVN424 multiple-dose PK in blood of PD subjects

Exploratory Objectives:

• To explore possible serum/plasma, DNA and/or RNA markers (e.g., drug metabolic enzyme and transporter polymorphisms) that may contribute to variability in CVN424 PK, safety or efficacy

Subject Population:

Male and female subjects, ages 30 to 80 years old, with idiopathic Parkinson's disease and motor fluctuations on stable doses of levodopa

Target Number of Subjects:	Number of Sites:
45 subjects per arm (total n=135 subjects)	Approximately 30 in the United States of America
Dose Level(s):	Route of Administration:
Planned dose levels are placebo, 50 mg, and 150 mg CVN424. Study drug dispensed as CVN424 suspension (or matching placebo) in amber colored bottles suitable for self-administered dosing.	Oral
Duration of Treatment:	Period of Evaluation:
Daily oral doses for 28 days.	Screening Period: up to 28 days
	Treatment Period: 28 days
	Follow-up Period: approximately 7 days
	Total Duration: Approximately 9 weeks

Main Criteria for Inclusion:

- 1. Male or female adult who is 30 to 80 years of age inclusive at study entry.
- 2. Has idiopathic Parkinson's disease, Hoehn and Yahr stages 2-4, and is on a stable dosage of levodopa. (Stable is defined as a dosage unchanged in the 30 days prior to randomization and, in the opinion of the investigator, able to continue the current regimen throughout the month-long study without undue inconvenience or harm.)
- 3. Experiences an average of at least 2 h total OFF time/day, and at least 1 h each day, per Patient Motor Diary over 2 days during Screening assessment.
- 4. The subject signs and dates a written informed consent form (ICF) and any required privacy authorization prior to the initiation of any study procedures.

Main Criteria for Exclusion:

- 1. Has atypical parkinsonism, severe disabling dyskinesia, or severe motor fluctuations that the investigator considers likely to interfere with study participation or assessments, or history of implant for Deep Brain Stimulation.
- 2. Poor concordance (<75%) of self-report with site rater on in-clinic Screening period Patient Motor Diary. Subjects with low concordance may be retested after further instruction, at investigator's discretion.
- 3. Screening period Patient Motor Diary scored at-home over 2 days demonstrates unacceptable quality of the diary, with more than 4 errors per day. (Assistance from caregivers is permitted if they also will be providing assistance with home Patient Motor Diary entries for Day 15 and 27 efficacy assessments.) Subjects with more than 4 errors per day may be retested after further instruction, at investigator's discretion.
- 4. Body mass index (BMI) at Screening <18.0 or >35.0 kg/m², inclusive.
- 5. Subject has evidence of CS neurologic or other disorder or impairment that, in opinion of Investigator, is reasonably expected to impact the ability of the subject to participate or to confound the study results.
- 6. Subject has current or recent (within 6 months) gastrointestinal disease that would be expected to influence the absorption of drugs (i.e., a history of malabsorption, any surgical intervention known to impact absorption [e.g., bariatric

Study No. CVN424-201 Page 12 of 73

Protocol v. 4.0 14 July 2021

surgery or bowel resection]).

- 7. Subject has a history of cancer or other malignancy, with the exception of low-grade cervical intraepithelial neoplasia, low-grade (low-risk) prostate cancer, or 5-year cancer-free survivors of basal or squamous cell carcinoma, higher-grade cervical intraepithelial neoplasia or prostate cancer.
- 8. Has a history of human immunodeficiency virus (HIV) infection.
- 9. Subject has a supine blood pressure outside the ranges of 80 to 160 mm Hg for systolic and 50 to 100 mm Hg for diastolic, confirmed with up to two repeat tests, at the Screening Visit; or symptomatic orthostatic hypotension, in the opinion of the investigator.
- 10. Subject has a resting heart rate outside the range 50 to 100 bpm, confirmed with up to two repeat tests, at the Screening Visit.
- 11. Positive urine result for illegal drugs (except cannabis) at Screening, or history of illegal drug use (except cannabis) or alcohol abuse within 1 year prior to the Screening Visit.
- 12. Subject has received any investigational compound (defined as a drug that has not been FDA-approved) within 30 days prior to the first dose of study medication, or within 5 half-lives of the investigational compound, whichever is greater.
- 13. Subject has, within the prior month, ingested any excluded medication, supplements, or food products listed in the Excluded Medications and Dietary Products table as listed in Table 2.
- 14. Male subjects who do not agree to all the following rules: when sexually active with female partner(s) of childbearing potential during the study and for 12 weeks after the last dose of study drug: a) use an acceptable method of birth control (condom with spermicide or surgical sterilization) and b) refrain from sexual activity with female partners who do not use an acceptable method of birth control. Barrier contraception (condom with spermicide) must be used by all male subjects who were not surgically sterilized at least 90 days prior to screening. Male subjects must also agree to refrain from sperm donation during the study and until 12 weeks after the last dose of study drug.
- 15. Female subjects who are pregnant or breastfeeding or plan to become pregnant or donate ova during the study or for 30 days after the last dose of study drug. Women of childbearing potential (WOCBP) also must be practicing an adequate method of birth control (e.g., oral or parenteral contraceptives, intrauterine device, barrier, abstinence).
 - *Definitions and acceptable methods of contraception are defined in Section 9.1.9, Contraception and Pregnancy Avoidance Procedure, and reporting responsibilities are defined in Section 9.1.10, Pregnancy.
- 16. Risk of suicide according to the investigator's clinical judgment or has made a suicide attempt in the previous 3 years.
- 17. Subject is a study site employee or an immediate family member of a study site employee.

In addition, subjects may not use any excluded medications, supplement, or food product as listed in Table 2 during the study.

- Safety assessments:

Safety assessments will include AEs, clinical laboratory results, vital signs and weight, physical examinations, electrocardiogram (ECG), Questionnaire for Impulsive-Compulsive Disorders (QUIP), and Beck Depression Inventory. AEs will be collected from signing of ICF. AEs with onset or exacerbation up until dosing on Day 1 will be scored as pretreatment events (PTEs), and AEs that occur from first dosing until 30 days after the last dose will be captured as a treatment-emergent AE (TEAE). Vital signs will be recorded at Screening and at least once at each Study Visit. On Day 1 and Day 8, vital sign assessments will be conducted predose [within 90 minutes prior to dosing], and at least hourly through 3 h post-dose. Vital signs will include oral temperature, blood pressure, respiration rate and heart rate. Triplicate orthostatic vital signs (blood pressure and heart rate) will be recorded 15 minutes apart at baseline. Orthostatic vital signs (non-triplicate) will be recorded pre-dose and at 3 h post-dose on Visit Days 1 and 8. Heart rate and blood pressure will be measured after at least 5 minutes supine and (when orthostatic vital signs are specified) again after 2 minutes standing. Additional monitoring of vital signs and ECGs may continue beyond 3 h post-dose at the discretion of Investigator.

Standard 12-lead ECGs will be recorded in triplicate at Screening and on Visit Days 1, 8, 27, and 35.

A description of safety assessments is provided in Section 9.1 and the full Schedule of Study Procedures is provided in Appendix

Study No. CVN424-201 Page 13 of 73

Protocol v. 4.0 14 July 2021

A.

- Efficacy assessments:

Efficacy assessments will include Patient Motor Diary (Hauser diary), Unified Parkinson's Disease Rating Scale (UPDRS), Epworth Sleepiness Scale, Clinical Global Impression (CGI), and Patient Global Impression (PGI).

- Determination of CVN424 concentration in plasma:

Plasma samples will be collected for the determination of concentrations of CVN424 as described in Section 9.1.13, PK Sample Collection.

PK parameters of CVN424 will be derived from the concentration-time data for evaluable subjects. The following PK parameters will be determined from concentrations of CVN424 in plasma: C_{min} at steady state (trough level on Day 22), C_{max} on Day 22, time to reach C_{max} on Day 22 (t_{max}), AUC from time 0 to 6 h (AUC₆), terminal elimination rate constant (λ_z), terminal elimination half-life ($t_{1/2z}$), apparent clearance (CL/F), and apparent volume of distribution (V_z /F).

- Pharmacogenomics:

One whole blood sample will be collected at Baseline for pharmacogenomic analysis; this will only be collected once per subject. A whole blood sample will be collected at pre-dose and 3 h post-dose on Day 1 for ribonucleic acid (RNA) pharmacogenomic analysis. The samples will be stored for no longer than 15 years after completion of the CVN424 study and/or until the drug development of CVN424 is no longer actively pursued by Cerevance or its collaborators. No samples will be stored for longer than permitted by the applicable law and samples will be destroyed upon notification from Cerevance. "Stored samples" in this context are defined as samples that are double coded (the samples are stripped of all personal identifying information but a key links the samples to the clinical data collected from the sample donor) and are used in the analysis of investigational drug or related drug.

The sampling of whole blood for pharmacogenomic and genotyping analysis is mandatory; every subject must sign the ICF in order to participate in this study. DNA samples can be used to identify markers (e.g., potential metabolites, or drug metabolic enzyme and transporter polymorphisms) that may contribute to variability in CVN424 PK, pharmacodynamics, or safety. Also, since pharmacogenomics is an evolving science, many genes and their functions are not yet fully understood. Future data may suggest a role of some of these genes in drug response, which may lead to additional hypothesis-generating exploratory research and diagnostic development on stored samples.

Endpoints:

The primary endpoint of this study will be:

Percentage of subjects with TEAE related to study drug

The secondary endpoints will include:

- Percentages of subjects with abnormal and clinically significant (CS) safety laboratory test results, ECG test results, or vital sign measurements at least once post-dose
- Change from baseline in 2-day average OFF time at Day 27 as recorded in the Patient Motor Diary over the two days prior to each visit

Additional and Exploratory endpoints will include:

- Change from baseline in UPDRS Part I at Day 27
- Change from baseline in UPDRS Part II at Day 27
- Change from baseline in UPDRS Part III at Day 27
- Change from baseline in UPDRS Part IV question 32 at Day 27
- Change from baseline in UPDRS Part IV question 33 at Day 27
- Change from baseline in CGI and PGI at Day 27

Study No. CVN424-201 Page 14 of 73

Protocol v. 4.0 14 July 2021

- Change from baseline in Epworth Sleepiness Scale at Day 27
- Change from baseline in 2-day average ON time without troublesome dyskinesia at Day 27
- Change from baseline in efficacy measures at Days 15 and 27
- Plasma PK parameters
- Possible characterization of plasma metabolites, or metabolic enzyme and transporter polymorphisms.

Statistical Considerations:

Safety:

Safety will be assessed among all subjects who receive at least one dose of study drug, classified according to the treatment actually received. AEs will be presented in listings, and TEAEs will be summarized as number of distinct events and the number and percentage of subjects experiencing a given class of AE as defined by the Medical Dictionary for Regulatory Activities (MedDRA) System Organ Class and Preferred Term. Individual results of laboratory tests (e.g., hematology, chemistry, urinalysis, and endocrine) will be listed and observed values and change from baseline will be summarized. Individual results of vital signs and weight will be listed and observed values and changes from baseline will be summarized. Individual results of quantitative ECG parameters from the 12-lead safety ECGs will be listed and observed values and changes from baseline will be summarized. All summaries will be performed by placebo, by CVN424 dose level, and for CVN424 overall. Subgroup analyses will assess the influence of selected demographic and disease-related characteristics. Physical exam findings will be presented in data listings.

Efficacy:

Efficacy will be assessed among all subjects who were eligible, randomized, and received at least one dose of study drug, classified according to the treatment actually received. Secondary tests of efficacy will assess subjects who were eligible, randomized, and judged compliant with treatment and follow-up as classified prior to breaking the blind. Serial assessments of average daily hours of OFF time as recorded in the Patient Motor Diary over the two days prior to each visit will be using mixed model for repeated measures (MMRM). The model will include fixed terms for treatment, visit, treatment x visit interaction and baseline measurement with subject-level unstructured covariance among repeated measurements. Other covariance structures may be used in case the model do not converge using unstructured covariance structure. Additional covariates may be included based on review prior to breaking the blind. The primary estimand of efficacy for each active dose vs. placebo will be the treatment-dependent difference in change from baseline to Day 27 and will be tested using linear contrasts of least-square means. Each comparison will test for significance at one-tailed p < 0.1 to control the overall type 1 error rate at 20% based on Dunnett's method for comparing two treatments to the same control. Additional contrasts will be used to test for a dose-dependent effect of treatment and to estimate dosage-dependent differences in change from baseline at all other visits. Additional and exploratory efficacy endpoints will be analyzed in the same model and using the same estimands. Subgroup analyses will assess the influence of selected demographic and disease-related characteristics.

PK Measures:

Concentrations of CVN424 in plasma will be summarized by dose level and by gender (if possible) over each scheduled sampling time using descriptive statistics. Individual plasma concentration data versus time will be presented in a data listing. PK parameters of CVN424 will be summarized by dose and by gender (if possible) using descriptive statistics.

Sample Size Justification:

The safety and tolerability of single- and repeated (7 daily) administration of CVN424, including doses higher than in the present study, were previously demonstrated in a study with 64 healthy volunteers (NCT03657030). The target sample size of 45 subjects per treatment arm (total N=135) is considered to be sufficient for the preliminary evaluation of CVN424 safety, tolerability and efficacy in a PD population. The study will have 90% power to detect at least one instance of any TEAE with an expected incidence of 0.10 per participant exposed at a given dosage of CVN424.

When the true effect of both dosages is zero, the study will have an 80% probability of declaring neither dosage of CVN424 significantly better than placebo at reducing OFF time based on the one-tailed p < 0.1 criterion, allowing 20% non-evaluable (e.g., loss to follow-up, incomplete data) and assuming a standard deviation (SD) of 3 h for the change in OFF time from baseline

Study No. CVN424-201 Page 15 of 73

Protocol v. 4.0 14 July 2021

to 27 days. When the true effect of a dosage is a reduction in average OFF time of at least 1.5 h, the study will have an 80% probability of declaring at least one dosage of CVN424 significant based on the one-tailed p < 0.1 criterion. By this construction, the study has 80% power to detect whether CVN424 does not reduce OFF time and 80% power to detect whether CVN424 at one or both of the two dosages tested reduces OFF time by at least 1.5 h.

Study No. CVN424-201 Page 16 of 73

Protocol v. 4.0 14 July 2021

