A first-in-humans safety study of CVN424 in 64 healthy volunteers has been completed (NCT03657030); the study findings are summarized in the Investigator's Brochure. In brief, CVN424 was safe and well tolerated when administered to healthy subjects as a single oral dose of between 1 mg and 225 mg, or when administered as 7 daily oral doses of between 25 mg and 150 mg. Study drug-related adverse events (AEs) were reported by 2 of 40 subjects (5.0%) overall in the single-dose cohorts (feeling hot; headache). Study drug-related AEs were reported by 2 of 24 subjects (8.3%) overall in the multiple-dose cohorts (dysphagia; chills). With one exception, all AEs were mild in severity; dysphagia of moderate severity led to treatment discontinuation in one subject after their third daily dose (75 mg). There were no severe or serious AEs, and all AEs had resolved by the end of the study. Administration of the first dose of CVN424 was associated with an elevation in group mean and median body temperature. These changes were detectable at 1 h post-dose (the earliest scheduled post-dose assessment), increased further by 6 h post-dose, and spontaneously returned to baseline by 24 h post-dose. The increases tended to be larger at higher doses but did not appear to be strictly dose-proportional. A trend of increase in heart rate while standing was also observed with a similar time course and relationship to dosage. These trends were not considered clinically significant, and no individual vital sign measurement was reported as an AE. In the multiple-dose cohorts, elevations in body temperature and heart rate were observed only after the first dose of CVN424, not following subsequent doses. No other trends in vital sign measurements

Study No. CVN424-201 Page 19 of 73

Protocol v. 4.0 14 July 2021

were noted. No treatment-related trends were observed in the clinical laboratory results or 12-lead electrocardiogram (ECG) measurements.

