9.1.6 Documentation of Concomitant Medications

Concomitant medication is any drug given in addition to the study medication. These may be prescribed by a physician or obtained by the subject over the counter. Concomitant medication is not provided by the sponsor. At each study visit, subjects will be asked whether they have taken any medication other than the study medication (used from signing of ICF through the end of the study), and all medication including vitamin supplements, over-the-counter medications, and oral herbal preparations, must be recorded in the eCRF. Documentation will include generic medication name, dose, unit, frequency, route of administration, start and end dates, and reason for use.

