9.3.1.2 Study Visit, Baseline and Randomization (Day 0)

All eligible subjects who are being enrolled will present to their local site for a Baseline and Randomization visit. Baseline efficacy and safety assessments will be performed, including (but not limited to) UPDRS, CGI, PGI, Questionnaire for Impulsive-Compulsive Disorders (QUIP).

Following baseline assessments, subjects' treatment assignment will be randomized using the online interactive response system.

Arrangements will be made for the subject to attend their Day 1 visit.

9.3.1.3 Study Visit, Day 1

A urine hCG pregnancy test will be performed for female subjects of childbearing potential; pregnant women must not receive study drug.

The first dose of study drug (CVN424 or placebo) will be administered under direction of site personnel. Subjects not randomized to placebo will initiate treatment with 50 mg CVN424. Vital signs will be assessed hourly through at least 3 h post-dose. Orthostatic vital signs (non-triplicate) will be recorded pre-dose and at 3 h post-dose. Triplicate ECG will be obtained prior to dosing and approximately 3 h post-dose. Additional monitoring of vital signs and ECGs may continue beyond 3 h post-dose at the discretion of the Investigator.

Investigator or their delegate will manage incident AEs according to their medical judgment. The first dose of CVN424 may elicit an increase in body temperature and heart rate lasting several hours. These signs can be expected to spontaneously resolve within 24 h post-dose, and to lessen with repeated dosing. Antipyretic medication (e.g., Acetaminophen Extended Release Caplets, 650 mg) can be administered for symptomatic relief of fever.

A blood sample for PK analysis will be collected pre-dose and at 3 h post-dose, according to Table 5.

Subjects will be given a 10 day supply of study drug (as suspension in amber colored bottles) to be taken home and stored under refrigeration until use. Study drug will be self-administered each morning through Day 27 ± 1 day.

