12.1.4.3 Vital Signs

Individual results of vital signs that are abnormal and CS will be summarized and listed. Observed values and changes from Baseline in vital sign measurements will be summarized by placebo, each CVN424 dose level and CVN424 overall. All vital sign data will be provided in the data listings.

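### Temperature on Days 1 and 8 is summarised as observed, but antipyretics are allowed and no clock time is listed for them, so a drug-related rise may be understated

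*Combined protocol and SAP*

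**What the plan says.** **Analysis.** Section 2.0 (Statistical Considerations, Safety) plans only listings and as-observed summaries: "Individual results of vital signs and weight will be listed and observed values and changes from baseline will be summarized". Section 12.1.4.3 says the same by arm: "Observed values and changes from Baseline in vital sign measurements will be summarized by placebo, each CVN424 dose level and CVN424 overall". Neither says what to do with a temperature taken after an antipyretic.

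**Expected effect.** Section 4.1 reports from phase 1: "Administration of the first dose of CVN424 was associated with an elevation in group mean and median body temperature". The rise was detectable at 1 h, "increased further by 6 h post-dose, and spontaneously returned to baseline by 24 h post-dose", and tended to be larger at higher doses. Sections 6.1 and 9.3.1.4 give limiting this vital-sign change as the reason for the step-up to 150 mg.

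**Permitted treatment.** Section 9.3.1.3 (Day 1) warns of the first-dose rise and then says: "Antipyretic medication (e.g., Acetaminophen Extended Release Caplets, 650 mg) can be administered for symptomatic relief of fever". The permission is not restricted to an arm.

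**Records.** Section 9.1.6 lists the concomitant-medication fields: "Documentation will include generic medication name, dose, unit, frequency, route of administration, start and end dates, and reason for use". Clock time is not among them. Times are collected for observed study-drug doses (Section 9.2), PK samples (Section 9.1.13.1) and adverse events (Section 9.6.1.2).

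**Readings.** On Days 1 and 8, vital signs are taken before dosing and at least hourly to 3 h after it. Later monitoring is at the investigator's discretion.

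**The concern.** Safety is the primary objective, and temperature is one of the two vital signs, with heart rate, that phase 1 showed CVN424 to move. The protocol permits a drug that lowers temperature to be given for the effect being measured, then averages every reading as if none had been given. If the drug causes the rise, treated subjects are more likely to be on CVN424, so any bias runs towards making the drug look better tolerated.

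Day 8 matters because it is the high-dose arm's first exposure to 150 mg, and its readings are the direct check on whether the step-up does its job. With readings an hour apart, a calendar date cannot show which of them followed an antipyretic. A later SAP can add a table, but it cannot recover a clock time that was never collected.

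**Working it through.** **No figure to reproduce.** The plan gives no size for the temperature change, no SD and no rate of antipyretic use. What follows is an illustration on assumed values.

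**Inputs**
- From the documents: 45 subjects per arm (Section 12.3); readings hourly to 3 h.
- Assumed: fA and fP, the shares of an active arm and of placebo given an antipyretic before a given reading; r, the resulting fall in treated subjects, 0.3 to 1.0 °C; SD of temperature change, 0.3 to 0.5 °C.

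**Step 1: bias.** Treating a share f of an arm lowers that arm's mean by f × r. The active-minus-placebo difference is therefore understated by (fA − fP) × r.

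| fA | fP | fA − fP | r = 0.3 °C | r = 1.0 °C |
|---|---|---|---|---|
| 0% | 0% | 0 | 0 | 0 |
| 2% | 0% | 0.02 | 0.006 | 0.02 |
| 10% | 2% | 0.08 | 0.024 | 0.08 |
| 25% | 2% | 0.23 | 0.069 | 0.23 |
| 50% | 5% | 0.45 | 0.135 | 0.45 |

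**Step 2: scale.** The 95% half-width for a difference between two arms is 1.96 × SD × √(2/45).
- SD 0.3: 1.96 × 0.3 × 0.2108 = 0.124 °C
- SD 0.4: 0.165 °C
- SD 0.5: 0.207 °C

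**Step 3: comparison.** At 10% versus 2% use, the bias stays below even the smallest half-width (0.08 against 0.124 °C). At 25% versus 2% it runs from about half the smallest half-width (0.069 / 0.124 = 0.56) to just above the largest (0.23 against 0.207 °C). So it is small at low use and matters only if roughly a quarter or more of an active arm is treated before the 1 to 3 h readings.

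**Step 4: a rough pointer from phase 1.** The temperature-like drug-related events named in Section 4.1 are one report of feeling hot and one of chills among 64 subjects: 2/64 = 3.1%. If that stood in for fA, with fP = 0, the bias would be 0.031 × 0.3 to 0.031 × 1.0, or about 0.01 to 0.03 °C. This is a weak proxy: those were healthy volunteers, and an event report is not antipyretic use.

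**Step 5: the clinically significant abnormality endpoint.** Section 5.2.2 counts a subject once if any post-dose vital sign qualifies. A post-dose reading that prompts an antipyretic is taken before it and stays in the data. Only a subject whose later, untreated reading would have been the first to qualify is lost.

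**The case against.** The case for leaving the plan alone has several sound parts.

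- **Users can be identified.** A reader might infer that nothing but dates is kept. That is wrong: drug, dose and reason for use are recorded, so subjects given an antipyretic for fever on a study day can be listed by arm. Only the order of events within the day is missing.
- **Treated fever should surface elsewhere.** Section 9.5.3 counts the need for treatment among the marks of an untoward finding, and adverse events carry start and stop times. Treated fever would ordinarily be an adverse event and, if judged related, would count in the primary endpoint. This stands, but the event's onset time is not the time the antipyretic was taken.
- **Use may be rare or late.** On the phase 1 trends the protocol says: "These trends were not considered clinically significant, and no individual vital sign measurement was reported as an AE". The rise was larger by 6 h than at 1 h, so treatment could follow the last scheduled reading, in which case the bias is zero.
- **Day 8 is less certain.** The antipyretic permission sits in the Day 1 text, and in phase 1 "elevations in body temperature and heart rate were observed only after the first dose of CVN424, not following subsequent doses". A reader might infer that subjects would take an antipyretic before the Day 8 visit; nothing supports this, and Section 7.3 asks subjects to consult before taking anything new. Day 8 stays in scope because it brings the step to 150 mg and investigators manage adverse events by their own judgment.
- **As-observed reporting is legitimate, and a SAP is promised.** No test on temperature is planned, and Section 12.1 defers methods to a SAP whose separate text is not in the document reviewed. It may already include a sensitivity display, but it could not supply the missing time.

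These points limit the size and reach of the problem. They do not remove the gap in data capture.

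**Conclusion.** The concern holds in a limited form. Readings taken after an antipyretic on Days 1 and 8 cannot be reliably identified from the listed fields, and no handling rule is stated. If use before the 1 to 3 h readings is higher in the active arms, the temperature rise may be understated.

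A reader might go further and conclude that the rise is understated, or that extreme values will drop out of the clinically significant abnormality endpoint. The documents support neither. They give no rate of use, the permission covers all arms under blinding, and the reading that prompts treatment is kept.

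The size is unknown. The figures in the table rest wholly on assumed rates of use and an assumed fall per treated subject, and zero is within the plausible range. This is an inexpensive improvement to safety reporting, not a flaw that threatens the trial's conclusions. Its urgency comes from the fact that the time cannot be recovered later.

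**What to change.** 1. On Days 1 and 8, record the clock time of any antipyretic taken that day (Section 9.1.6 and the concomitant-medication eCRF page).
2. In Section 12.1.4.3, with matching wording in the study summary, flag temperature readings taken after an antipyretic on the same day.
3. Tabulate antipyretic use by arm and visit.
4. Present temperature by arm as observed and again with flagged readings set aside. Carrying forward the subject's highest earlier post-dose value that day is an optional further display.

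**Cost.** One eCRF time field at two visits and one extra table. Each alternative display carries its own assumption. Setting readings aside drops later values from subjects who may be the warmest, and carrying a value forward can fall short if temperature was still rising. The as-observed summary should therefore remain the main one. Nothing here changes who may receive an antipyretic.
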